## **13.0 Withdrawal of Subjects\***

A participant meets the criteria for “premature discontinuation” if they withdraw from the study before completion. Premature discontinuation would include participants who decide to voluntarily end their participation early for any reason, as well as participants who may be withdrawn from the study based on an adverse response to the intervention and consultation with the MD, [name]. Participants may choose not to attend some sessions or complete all assessments, but they will not be compensated for assessments they do not complete. Participants will not be involuntarily removed from the study for missing sessions or assessments if they indicate that they would like to remain in the study. If a participant fails to attend 2 consecutive appointments and assessments without notifying the study team, we will reach out to them up to 3 times via phone and/or email to assess their interest in continuing in the study. No response from the participant will be considered a premature discontinuation, and they will be withdrawn from the study. Completion represents completing the assessments in addition to the intervention. There are no alternative treatments or procedures for participants that choose to withdraw from the study, other than care as usual. Participants will be reminded that their participation is voluntary and they may choose to end participation in the study at any time.

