## 2.0 Objectives\*

- **Objective 1:**

Assess feasibility and acceptability of all protocol components of a pilot pragmatic trial testing a 6-week telehealth KNA program compared to a KN information only group for older adults with possible or pre-MCI in the community and at a senior health clinic to prepare for a full-scale trial.

Specifically, we will examine the feasibility of the recruitment, retention, assessment, electronic health record (EHR) downloads, and intervention delivery methods through the FSU SeniorHealth™ clinic. If we determine it is not feasible to recruit the full sample through this clinic, we will expand recruitment to the community.

We hypothesize that

- *The study protocol (MI-CBT KNA program) will result in high patient retention (90%) and patient attendance of intervention sessions (80%), and*
- *A centralized MI-CBT telehealth delivery approach will be associated with high intervention acceptability ratings from patients and key stakeholders.*
- *MI-CBT KNA program will result in higher adherence to KN compared to the KN information-only group as evidenced by higher levels of ketones at week 6 of the intervention using at-home ketone urinalysis test strips.*

To test these hypotheses, we will use a mixed methods approach using qualitative interviews, quantitative measures of patient satisfaction with the intervention (using the Client Satisfaction Questionnaire) and provider perception of the overall fit of the intervention in the clinic, and of patient intervention attendance and study attrition. Qualitative data from providers and patients will be thematically coded to further examine acceptability and barriers to implementation.

- **Objective 2:**

Assess signal of initial effect of the KNA program on important clinical outcomes and adherence relative to a KN information-only condition.

We hypothesize that *patients in the KNA condition, relative to the KN-only condition, will show 1) higher rates of clinically significant improvements on the RBANS total scale scores, improvements in daily functioning (FSQ), decreases in patient CAIDE risk score, improvements in HbA1C levels and comprehensive metabolic panels, and improvements in self-reported pain using the Rolland-Morris Pain scale, and 2) improved adherence to KN, as evidenced by higher levels of measurable urine ketones in the KNA condition compared to the KN-only condition.*

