Baseline Assessment (Time 1). In addition to embedded EHR and other health record data, we are collecting additional data to evaluate the personal impacts of the intervention. This in-person assessment will include: the Repeatable Battery of Neuropsychological Status (RBANS update – form A), GAS, PHQ-9, FSQ, ISEL, MSQ, CAIDE risk score, OPQOL, GSE, PSQI, SCOFF, social support, self-efficacy, a verbal pain descriptor scale, the Brief Pain Inventory, The WOMAC-Pain scale, the PANAS, PSS, the WHY-MPI, and the Roland-Morris Pain and Pain-related Disability scale, a fasting blood draw for a comprehensive metabolic panel and HbA1C (completed by a certified medical assistant), a weight and body composition assessment, and basic vitals (blood pressure and heart rate). Participants will be scheduled in the morning for these assessments in order to allow approximately 10-hour fasting for the blood draw. This assessment will be completed in-person following COVID-19 precautions (described in section 14), and patient participants will be compensated \$30 for their time.

Post-intervention Assessment (Time 2). Participants will complete this assessment in the final weeks of the program, in order to assess participants when they are in ketosis. Participants will be asked to return their ketone logs either electronically, reported over the phone, or via mail to the study PI. The research team will complete qualitative interviews with participants to collect information about barriers and facilitators to completing the program and adhering to KN. Participants will complete the RBANS update – Form B, the PHQ-9, FSQ, MSQ, GAS, CAIDE risk score, OPQOL, PSS, PSQI, social support (ISEL), self-efficacy (GSE), group cohesion, a verbal pain descriptor scale, the Brief Pain Inventory, The WOMAC-Pain scale, the PANAS, the Roland-Morris Pain and Pain-related Disability scale, the WHY-MPI, and participants' global impression of change, a second fasting blood draw for comprehensive panels (completed by a certified medical assistant), a weight and body composition assessment, and basic vitals (blood pressure and heart rate). Participants will be scheduled in the morning for these assessments in order to allow approximately 10-hour fasting for the blood draw. This assessment will be completed in-person following COVID-19 precautions, and patient participants will be compensated \$30 for their time.

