Post-intervention Assessment (Time 3). Patient participants will complete this assessment approximately 3 months after completing the intervention program, in order to assess long-term maintenance. The research team will complete qualitative interviews with participants to collect information about barriers and facilitators to adhering to KN long-term. Participants will complete the RBANS Update – form C, the PHQ-9, FSQ, MSQ, GAS, CAIDE Risk score, OPQOL, PSQI, social support (ISEL), self-efficacy (GSE), a verbal pain descriptor scale, the Brief Pain Inventory, The WOMAC-Pain scale, the PANAS, PSS, the WHY-MPI, the Roland-Morris Pain and Pain-related Disability scale, the Client Satisfaction Questionnaire (8-item), and participants' global impression of change in pain. This assessment will be completed in-person following COVID-19 precautions and patient participants will be compensated \$30 for their time.

Participants who express barriers to completing the 3-month post-intervention assessment in person will have the option to complete this assessment remotely if they

choose to. In the even that a participant chooses to complete the Time 3 assessment remotely, the following procedures will be conducted: a research assistant will schedule a phone call with the participant at a time that is convenient to them to complete the qualitative interviews with participants and collect self-reported height, weight, and ketone test (if available); participants will be asked to complete questionnaires via REDCap by following a link to the survey that will be emailed to them by a team member; lastly, due to the nature of the RBANS, participants who choose to complete the Time 3 assessment remotely will not be asked to complete the RBANS Update – form C. Participants will receive the same amount of compensation, \$30, for their time upon completing the assessment procedures.

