## **14.0 Risks to Subjects\***

We are only recruiting individuals without unstable chronic medical conditions for this nutrition intervention (e.g., significant gallbladder problems, cancer, Type 1 diabetes). Further, participants who are underweight based on BMI will be excluded ( $BMI < 19$ ). Individuals with these conditions will be screened out in the initial call prior to completing the consent process.

Thus, primary risks associated with changing diet may include, gastrointestinal upset (i.e., bloating, diarrhea, gas, and constipation), change in weight, headache, and fatigue. Participants will be closely monitored by the study team on a weekly basis to assess any adverse response to the diet. If a significant adverse response is reported or identified, the team will consult the MD consultant on the team, [name], for a clinical decision.

Participants will be asked to provide two fasting blood samples for assessment of metabolic panels and HbA1c. There may be slight discomfort when inserting the needle. Even with precautions, minor bruising and swelling around the puncture site can occur. Because every person’s veins are different, and veins move frequently, bruising can occur even with the most experienced phlebotomists. Participants will be required to fast for 8-12 hours prior to the blood draw. The primary risks associated with fasting may include lightheadedness. Thus, we will provide snacks for participants after the blood draw is complete.

Other risks include mental fatigue from completing some potentially challenging cognitive tasks.

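### Section 13.0 lets an adverse response end study participation and not only the diet, and nothing provides for Time 2 and Time 3 assessment of participants withdrawn this way

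*Protocol*

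**What the plan says.** Section 13.0 (Withdrawal of Subjects) defines a single exit category, premature discontinuation, which means leaving the study before completion. It covers people who stop voluntarily "as well as participants who may be withdrawn from the study based on an adverse response to the intervention", after consultation with the MD. The same section defines the other outcome: "Completion represents completing the assessments in addition to the intervention".

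Section 13.0 has one provision for staying in: "Participants will not be involuntarily removed from the study for missing sessions or assessments", provided they say they want to remain. It does not mention stopping the diet or adverse responses. On what follows withdrawal it says only: "There are no alternative treatments or procedures for participants that choose to withdraw from the study, other than care as usual".

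Section 14.0 (Risks to Subjects) sets the route by which a case is handled: "If a significant adverse response is reported or identified, the team will consult the MD consultant on the team", for a clinical decision. The possible decisions are not listed.

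The assessments at stake are in Section 6.0. Time 2 falls in the last weeks of the program, "in order to assess participants when they are in ketosis". Time 3 comes about three months after the program. It may be done remotely, but remote participants "will not be asked to complete the RBANS Update".

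Section 2.0 hypothesises 90% retention, and Section 4.0 lists study attrition among the feasibility measures.

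**The concern.** Stopping a treatment and stopping follow-up are separate events, and a trial can usually allow the first without the second. Here the only consequence of an adverse response that the protocol names is leaving the study. The case is foreseeable: Section 14.0 lists gastrointestinal upset, weight change, headache and fatigue as the main risks of the diet.

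Two things are at stake. First, the participants lost would be those who reacted badly to the intervention, so their Time 2 and Time 3 scores would be missing for a reason connected with it. Second, retention is a headline feasibility result. A participant who would willingly have come to the assessments, but was withdrawn for an adverse response, would look like a participant the study failed to retain. These are different problems for the full-scale trial.

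**Working it through.** **Step 1. Does any other section provide the missing route?**

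| Place | What it provides | Does it keep an MD-withdrawn participant in follow-up? |
|---|---|---|
| Section 5.0, KNA Weeks 2-4 | Stepwise carbohydrate reduction, the same for everyone, to prevent adverse responses | No; preventive only |
| Section 5.0, KNA Weeks 5-6 | Carbohydrate target adjusted to ketone level and macronutrients | No; not based on tolerance |
| Section 6.0, Time 2 | Assessment while in ketosis | No; gives no instruction for someone taken off the diet |
| Section 6.0, Time 4 | Health-record download with the Time 0 items | In part at most; might recover some laboratory or FSQ values, but RBANS is not a listed item |
| Section 13.0, stay-in provision | Missed sessions or assessments | No; does not cover withdrawal for an adverse response |
| Section 14.0 | Undefined clinical decision | Not excluded, but not described |

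No section supplies it. Where the withdrawal option is used, the Time 2 and Time 3 RBANS, FSQ and pain scores and the Time 2 metabolic panel would ordinarily not be collected.

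**Step 2. The retention allowance.** Inputs: 90% (Section 2.0), 30 per arm (Section 12.0), and a minimum of 40 enrolled (Section 11.0), taken as 20 per arm.

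- Arm of 30: 0.90 × 30 = 27 retained, so 30 − 27 = 3 losses allowed.
- Arm of 20: 0.90 × 20 = 18 retained, so 2 losses allowed.
- All 60: 0.90 × 60 = 54 retained, so 6 losses allowed.

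**Step 3. Share of the allowance used.** The protocol gives no rate of adverse-response withdrawal. Assume 1 to 3 per arm of 30, or 1 to 2 per arm of 20.

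- Share of the arm lost: 1/30 = 3.3% to 3/30 = 10%; 1/20 = 5% to 2/20 = 10%.
- Share of the allowance used in an arm of 30: 1/3 to 3/3.
- Top of the assumed range plus one other loss: (30 − 3 − 1)/30 = 86.7%, which misses the target. With the three kept in follow-up: (30 − 1)/30 = 96.7%, which meets it.
- The same at 20 per arm: (20 − 2 − 1)/20 = 85% against (20 − 1)/20 = 95%.

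**Step 4. Chance of meeting the target.** Let d be other dropout and a the proportion withdrawn for an adverse response, both assumed. The true retention probability is p = (1 − d)(1 − a), and the number retained is binomial.

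| | a = 0% | a = 3% | a = 5% | a = 10% |
|---|---|---|---|---|
| At least 27 of 30, d = 5% | 0.94 | 0.79 | 0.67 | 0.35 |
| At least 54 of 60, d = 5% | 0.97 | 0.81 | 0.63 | 0.21 |
| At least 54 of 60, d = 10% | 0.61 | 0.35 | 0.21 | 0.05 |

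The column a = 0% is the case in which everyone affected stays in follow-up.

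**Step 5. Effect on the clinical outcomes.** Assume 9 participants in an arm of 30 are observed to move to the normal RBANS range.

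- One missing: observed 9/29 = 31.0%; possible range among those randomised 9/30 = 30.0% to 10/30 = 33.3%.
- Three missing: observed 9/27 = 33.3%; possible range 9/30 = 30% to 12/30 = 40%.
- Width of the bounds on the difference between arms: (1 + 1)/30 = 6.7 points to (3 + 3)/30 = 20 points. These are worst-case bounds.
- Mean score, if those withdrawn would have done 0.5 SD worse (assumed): (1/30) × 0.5 = 0.02 SD to (3/30) × 0.5 = 0.05 SD within an arm. The shift cancels between arms if both lose equally.

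**The case against.** The case on the other side is substantial, and most of it stands.

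- **Leaving the diet is not leaving the study.** Participants follow the diet at home, adherence is itself an outcome, and no section makes it a condition of staying in. A reader might infer that anyone who cannot tolerate the diet is dropped. The document does not say so: someone who eases the diet or skips sessions may already remain. The gap is confined to those the MD withdraws.
- **The rule is discretionary.** Section 13.0 says such participants may be withdrawn, and the clinical decision in Section 14.0 could include easing or pausing the diet. This stands, but neither section names that option or the follow-up that would go with it.
- **The care-as-usual sentence does not bar follow-up.** It concerns treatments and procedures for people who choose to leave. It should not be read as ruling out outcome assessment after a clinician-led withdrawal.
- **Retention is not formally defined.** A reader might infer that the protocol requires these withdrawals to count against the 90%. It does not tie premature discontinuation to that figure. Counting them is the natural reading, not a stated rule. The definition, and reporting by reason, may be left to the SAP.
- **Bias in favour of one arm is not shown.** Both arms follow the diet, so neither the direction nor the size is known. Section 2.0 also plans visual examination of the clinical outcomes, without significance tests.
- **The consent form was not seen** and may say more.

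The core does not yield to these points. A SAP can choose a missing-data method, but it cannot supply RBANS or pain scores that were never collected. Whether they are collected is settled by the withdrawal section of the protocol.

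**Conclusion.** The point holds for participants whom the MD withdraws for an adverse response. For them the rule as written ends follow-up as well as the diet, and no other section restores the Time 2 and Time 3 assessments.

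The effect on a mean clinical score is likely small. The effect on the retention result could be decisive, because the allowance is only 3 losses in an arm of 30. Every figure beyond that allowance and its counterparts for 20 and 60 participants rests on assumed numbers of withdrawals, other dropouts, RBANS responders or SD shifts, since the protocol gives none of them. This is a cheap improvement worth making before enrolment is complete. It does not undermine the pilot. Confidence is medium, because the frequency is unknown and the MD's discretion may in practice already be used as proposed here.

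**What to change.** Change Section 13.0, and align the consent form if it says otherwise. Suggested wording:

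> If the MD stops or eases the diet because of an adverse response, the participant will be asked to remain in the study and to complete the weekly surveys, Time 2 and Time 3 on the planned schedule, counted from program start, whether or not in ketosis. The blood draw is done only if medically suitable. Time 3 is preferably in person, so that the RBANS is completed. Follow-up ends only if the participant withdraws consent or cannot be reached.

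The cost is a few sentences, some staff time, and payments that a completing participant would have received anyway. Each person kept costs $60 for Time 2 and Time 3 (2 × $30) plus $20 per remaining program week: 60 + 20 × 1 = $80 with one week left, and 60 + 20 × 5 = $160 with five left. For an assumed 2 to 6 people across both arms, this is 2 × 80 = $160 to 6 × 160 = $960. Some will decline, so part of the loss will remain.

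### The only named patient satisfaction scale is given about three months after the program, so anyone who leaves earlier never rates it and satisfaction is probably overstated

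*Protocol*

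**What the plan says.** Protocol section 2.0, Objective 1, hypothesises that the MI-CBT telehealth approach "will be associated with high intervention acceptability ratings from patients and key stakeholders". The same section names the Client Satisfaction Questionnaire as the quantitative measure of patient satisfaction. It sets no numeric threshold for a high rating. Retention has a target of 90% and session attendance a target of 80%.

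In section 6.0 the eight-item questionnaire appears in one assessment list, Time 3. Of that visit the protocol says: "Patient participants will complete this assessment approximately 3 months after completing the intervention program". The scale is not in the Time 2 list, which belongs to the final weeks of the program, and it is not in the weekly survey described in sections 5.0 and 6.0. The Assessment of Fit Scale at Time 4 is completed by providers.

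Section 13.0 describes three ways out before Time 3:

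- Participants may end participation voluntarily.
- There are "participants who may be withdrawn from the study based on an adverse response to the intervention", after consultation with the study physician.
- The no-reply rule begins "If a participant fails to attend 2 consecutive appointments and assessments without notifying the study team". Up to three contact attempts follow, and then "No response from the participant will be considered a premature discontinuation, and they will be withdrawn from the study".

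Section 13.0 also says that "Participants will not be involuntarily removed from the study for missing sessions or assessments", provided they say they wish to stay. No section offers Time 2 or Time 3 to someone who has been withdrawn. The remote Time 3 option is described for those with difficulty attending in person.

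**The concern.** The acceptability hypothesis is part of the primary objective, and it concerns the level of satisfaction in a program, not only a contrast between arms. A level is distorted by selective loss even when both arms lose the same share. If people who stop the diet, disengage or have an adverse response are less satisfied than those who stay, the observed mean describes the stayers and overstates the view of everyone who started.

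This arises from what is collected. A later analysis can put bounds on ratings that were never requested, but it cannot recover them. It also matters for the pilot's purpose, because the acceptability result feeds the decision on a full-scale trial.

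**Working it through.** The protocol gives no figure for satisfaction, so there is none to reproduce. The steps below size the problem under stated assumptions.

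**Inputs.** From the protocol: 30 participants per arm (section 12.0), 90% retention and 80% attendance (section 2.0), 6 or 7 sessions (sections 1.0 and 5.0). Assumed: leavers would score g = 0.5 to 1.0 SD below stayers; the share missing at Time 3 is m = 10% (treating the retention target as applying through Time 3) or 20%.

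**1. Overstatement of the mean.** If stayers average S, the mean over all starters is (1 − m)S + m(S − g) = S − mg. The observed mean S is therefore too high by m × g. The standard error of one arm's mean, in SD units, is 1/√(30(1 − m)).

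| Missing share m | Overstatement, g = 0.5 | Overstatement, g = 1.0 | Standard error |
|---|---|---|---|
| 10% (3 of 30) | 0.05 | 0.10 | 1/√27 = 0.19 |
| 20% (6 of 30) | 0.10 | 0.20 | 1/√24 = 0.20 |

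**2. Bounds without assuming a gap.** Take both arms together and suppose about 90% of raters are satisfied (assumed).

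- At 90% retention, 54 of 60 rate and 49 are satisfied (90.7%). The share among all 60 lies between 49/60 = 81.7% and (49 + 6)/60 = 91.7%.
- At 80% retention, 48 rate and 43 are satisfied (89.6%). The share lies between 43/60 = 71.7% and (43 + 12)/60 = 91.7%.

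**3. How much is due to the no-reply rule.** Let p = 0.2 be the chance of missing a session (the 80% attendance target), with misses independent and unannounced (assumed). The chance aₙ of no two misses in a row over n sessions follows aₙ = 0.8aₙ₋₁ + 0.16aₙ₋₂, with a₀ = a₁ = 1.

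- 1 − a₆ = 0.164, or 4.9 of 30.
- 1 − a₇ = 0.193, or 5.8 of 30.

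These are chances of being contacted, not of being withdrawn. If 25% to 50% then do not answer (assumed), 1.2 to 2.9 of 30 are withdrawn. Multiplied by the gap, that is 1.2/30 × 0.5 = 0.02 to 2.9/30 × 1.0 = 0.10 SD, even if all of them would otherwise have given a rating. If only a third to a half would have done so (assumed), the part due to the rule is about 0.01 to 0.05 SD. Announced misses lower these figures. So does a literal reading of the trigger, under which assessments must be missed as well as appointments.

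**4. What an earlier or exit rating would recover.** If a share r of those otherwise missing give a rating, the remaining overstatement is mg − mrg/(1 − m + mr). With r between 1/3 and 1/2 (assumed):

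- m = 0.1, g = 0.5: 0.05 falls to 0.032 (r = 1/3) or 0.024 (r = 1/2).
- m = 0.2, g = 1.0: 0.20 falls to 0.123 (r = 1/3) or 0.089 (r = 1/2).

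**The case against.** The strongest reply is that section 13.0 already goes far towards separating missed sessions from leaving the study. Participants may skip sessions or assessments, and anyone who answers a contact and wants to stay is kept. Time 3 can be done remotely. People who ignore up to three calls or emails are also the least likely to return a questionnaire, so for them the rule mostly labels a loss that would happen anyway. This stands. A reader might infer that the withdrawal rule is the main cause of the bias, but the text and step 3 above do not support that.

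A reader might also infer that the rule acts unequally between arms, because the KN-only meetings are described both as something participants are asked to attend and as optional. The protocol does not say whether a missed KN-only meeting counts, so no direction can be given. The acceptability hypothesis concerns the MI-CBT arm in any case. That wording should be reconciled as a separate matter.

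It is also fair that leavers are not invisible. Attrition and attendance are Objective 1 outcomes, and the weekly surveys and Time 2 interviews collect barriers and facilitators. This softens the concern but does not remove it. None of these is a satisfaction scale, and those who leave before Time 2 are not offered that interview.

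Finally, a rating after the program is defensible, because Time 2 can fall before the last session. That is a reason to keep Time 3 as a repeat, not a reason to have no earlier rating.

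**Conclusion.** The point holds in a limited form. The only named patient satisfaction scale for a primary-objective hypothesis is collected about three months after the program, and only from those still in the study. The resulting mean is probably too high. The direction rests on the assumption that leavers are less satisfied, which is plausible but which the protocol does not establish.

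The size is unknown. Under the assumed gap of 0.5 to 1.0 SD it is 0.05 to 0.10 SD at the loss the protocol itself expects, about a quarter to a half of one arm's standard error. It approaches the standard error only at 20% missing with the larger gap. A reader might infer that the satisfaction result would be uninterpretable. The documents do not support that, since the expected loss is 10% and attrition is reported beside it. This is an inexpensive improvement to a primary-objective measure, not a flaw that undermines the trial. Confidence is moderate.

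**What to change.** 1. Add the CSQ-8 to the week-6 online survey or to Time 2, and offer it at early exit to those willing. Keep Time 3 as a repeat.
2. In section 13.0, record stopping the program separately from leaving assessment. Unless consent is withdrawn, keep inviting those who stopped to Time 2 and Time 3, including the remote Time 3 option. All clinical decisions stay with the study physician.

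The cost is amendment wording, eight more items at an existing contact, and a few more contacts, some of which will go unanswered. The satisfaction figure may look less favourable, and for some participants a week-6 or Time 2 rating will come before the last session.
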